11.6 Disease-Related Signs and Symptoms

Reporting of disease related or DMD-related signs and symptoms as AEs are based on the investigator's clinical judgment. However, progression of symptoms and signs associated with DMD that is inconsistent to the usual course of the disease should be reported as an AE in the eCRF and source documentation.

11.7 Reporting

11.7.1 Adverse Event Reporting

All AEs occurring during the course of the study (starting from signing informed consent to study completion) will be collected on the AE eCRF. Each AE is to be evaluated for duration, severity, seriousness, and causal relationship to the investigational product. For each AE, the following information will be recorded:

- Description of the event (e.g., headache),
- Date of onset,
- Date of resolution (or that the event is continuing),
- Action taken as a result of the event,
- Seriousness of the event,
- Severity of the event,
- Outcome of the event, and
- Investigator's assessment of relationship to investigational product.

A cluster of signs and symptoms that results from a single cause should be reported as a single AE (e.g., fever, elevated WBC, cough, abnormal chest x-ray, etc., can all be reported as "pneumonia").

The investigator will carefully evaluate the comments of the participant and the response to treatment in order that he/she may judge the true nature and severity of the AE. The question of the relationship of AE to investigational product administration should be determined by the Investigator or study physician after thorough consideration of all facts that are available.

Clinically significant changes from time of ICF will be documented as AEs on the AE eCRF. Clinically significant changes are physical findings that have medical relevance and may result in an alteration in medical care.

11.7.2 Adverse Events of Special Interest Reporting

Adverse events of special interest should be promptly recorded in the eCRF so that the DSMB and medical monitor are notified. Such events will be reviewed by the DSMB and medical monitor to enable consideration of implications for other participants.

11.7.3 Serious Adverse Event Reporting

All SAEs occurring from the time of informed consent until the follow-up telephone call, 30 days following the last administration of study drug must be reported to the designated CRO and the sponsor within 24 hours of the knowledge of the occurrence. This includes death due to any cause and whether or not the SAE is deemed drug-related or expected. After the 30-day reporting window, any SAE that the investigator considers related to study drug must also be reported.

To report the SAE, the investigator is to complete the SAE form electronically in the electronic data capture (EDC) system for the study. If the event meets serious criteria and it is not possible to access the EDC system, the investigator is to send an email, phone or fax the event to the designated CRO within 24 hours of awareness. When the EDC system becomes available, the SAE information must then be entered within 24 hours of the system becoming available.

The investigator is required to submit SAE reports to the IRB or IEC in accordance with local requirements.

11.8 Serious Adverse Event Follow-Up

SAEs will be followed by the site investigator until resolution or until the investigator determines that follow-up is no longer medically necessary.

Follow-up information, or new information regarding an ongoing SAE, must be provided promptly to the CRO within 24 hours of knowledge of the new or follow-up information. The CRO will forward the information to the sponsor, and the medical monitor.

11.9 Expedited Reporting to Regulatory Authorities

The NS Pharma designated CRO is responsible for reporting all relevant information about suspected unexpected serious adverse reactions (SUSARs) that are fatal or life-threatening as soon as possible to the applicable regulatory authorities in all the Member States concerned, and to the Central Ethics Committee, and in any case no later than 7 days after knowledge by the

CRO of such a case. All other SUSARs will be reported to the applicable regulatory authorities concerned and to the Central Ethics Committee concerned as soon as possible but within a maximum of 15 days of first knowledge by the sponsor/designee.

The NS Pharma designated CRO will also report any additional expedited safety reports required in accordance with the timelines outlined in country-specific legislation.

The NS Pharma designated CRO will also inform all investigators as required per local regulation. Reports of all applicable SUSARs must be communicated as soon as possible to the appropriate IRB/IEC and/or reported in accordance with local laws and regulations.

Investigators should file written documentation of IRB/IEC notification for each report to the designated CRO as applicable.

The sponsor must report any suspected adverse reaction to the study drug, that is both serious and unexpected, or any SAEs suspected to be related to the CVA port, to the US FDA, Health Canada (21 CFR 312.32(c)(1)(i) and C.05.014, respectively), and other national and local health authorities.

11.10 Monitoring and Follow-Up of Adverse Events

Participants who experience AEs will be monitored with relevant clinical assessments and laboratory tests, as determined by the investigator. All follow-up results are to be reported to the medical monitor. Any actions taken and follow-up results must be recorded either on the appropriate page of the eCRF or in appropriate follow-up written correspondence, as well as in the participant's source documentation. Follow-up laboratory results should be filed with the participant's source documentation.

For all AEs that require the participant to be discontinued from the study, relevant clinical assessments and laboratory tests must be repeated at appropriate intervals until final resolution or stabilization of the event(s).

Any AEs that are unresolved at the participant's last AE assessment in the study are followed up by the investigator or designee for as long as medically indicated, but without further recording in the eCRF. The sponsor and designated CRO retain the right to request additional information for any participant with ongoing AEs/SAEs at the end of the study, if judged necessary.

11.11 General Monitoring and Management of Abnormal Clinical Laboratory Findings

It is the investigator's responsibility to review the results of all laboratory tests as they become available and to sign and date the results indicating review. For each laboratory test outside of the laboratory normal range, the investigator must ascertain if this represents a clinically significant change from baseline for the individual participant. The investigator may repeat a laboratory test or request additional tests to verify results of the original laboratory test.

If a laboratory value is determined to be an abnormal and clinically significant change from baseline for the participant, the investigator should determine if it qualifies as an AE, and if so, an appropriate eCRF will be completed. All clinically significant laboratory abnormalities occurring during the study and that were not present at baseline should be followed and evaluated with additional tests if necessary, until diagnosis of the underlying cause, or resolution.

11.11.1 Monitoring of Renal Function and Urine Analyses

All scheduled first morning void urinalyses will include urine dipstick protein to be performed at the site. If first morning void urine dipstick protein $\geq 2+$, UPCR ≥ 0.5 mg/mg, or

UPCR $\geq 2 \times$ baseline, a first morning void urine dipstick protein will be repeated within 1 week.

If 1 or more of these criteria are met again on the repeat test, a 24-hour urine sample will be collected within 1 week of the results to assess protein and creatinine. If proteinuria on a 24-hour urine sample is ≥ 300 mg/day, the patient will be referred to a pediatric nephrologist.

In addition, any instances of hematuria or other potentially clinically significant abnormalities on urinalysis will be confirmed at the following week's visit, or sooner at discretion of the investigator. Confirmed clinically significant treatment-emergent abnormalities will be recorded as AEs and discussed with the medical monitor. Abnormalities will be monitored and evaluated with additional tests or consultations, if necessary, until the underlying cause is determined, or the event is brought to an acceptable resolution. Additional clinical and laboratory information may be collected and documented in order to better characterize abnormalities and identify etiology and appropriate management. Potential need for interruption or discontinuation of study drug should be discussed with the medical monitor and sponsor.

If serum cystatin C $\geq 1.5 \times$ baseline, or if serum creatinine $\geq 2 \times$ baseline and ≥ 0.3 mg/dL, the test will be repeated within 1 week of the results. If either of these criteria are met again on the repeat test, the patient will be referred to a pediatric nephrologist.

To help relate creatinine and cystatin C measurements to GFR in patients with DMD, GFR will be determined using an exogenous tracer test, if available, at the Pre-Infusion Visit and Week 49 (or at early termination, if applicable). This should be done per standard of care at the institution.

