9.14.1 Sample Collection, Storage, and Shipping

Each participant will have blood drawn and urine collected for the blood and urine laboratory safety assessments as listed/described in the sections below and the schedule of study assessments ([Table 1](#) and [Table 2](#)), including hematology, chemistry, urinalysis, 24-hour urine analysis, urine cytology, exogenous tracer GFR, anti-dystrophin antibody, anti-viltolarsen antibody, and viral antigen and antibody testing.

Blood draw volumes will be 8.5 to 24.0 mL per day at screening, Day 1, Weeks 3, 5, 9, 13, 17, 21, 25, 37, 49, and EOT, totaling up to approximately 163.5 mL over the course of the study. No more than 47.0 mL will be drawn in a 4-week period.

For post screening urinalyses, patients will collect a first morning void urine sample on the date of the specified visit and bring it to the site according to the schedule of study assessments ([Table 1](#) and [Table 2](#)). Analysis of the sample will include urine dipstick protein to be performed at the site. An aliquot will also be sent to the central laboratory for urinalysis (see [Table 3](#) for a list of the laboratory analytes that will be measured for all urinalyses, including the first morning void urinalysis).

If first morning void urine dipstick protein $\geq 2+$, urine protein to creatinine ratio (UPCR) ≥ 0.5 mg/mg, or UPCR $\geq 2 \times$ baseline, a first morning void urine dipstick protein will be repeated within 1 week. If 1 or more of these criteria are met again on the repeat test, a 24-hour urine sample will be collected within 1 week of the results to assess protein and creatinine. Caregivers will be provided a diary to enter void times during the 24-hour collection period. When obtaining this 24-hour urine, the patient will be asked to urinate in the toilet immediately after

waking up on the day of the test. This time will be recorded in the diary as the start time.

Directions will be provided for collection throughout the test, and documentation of all subsequent voids will be recorded in the diary through the first sample immediately after awakening on the following morning, as close to 24-hours later as possible. Refer to [Section 11.11.1](#) for additional details on monitoring of renal function and urine analyses.

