 - Dipstick protein (to be performed by the site on the first morning void urine samples)
- 24-Hour Urine Analysis
 - Protein (benzethonium chloride method)
 - Creatinine
- Urine Cytology
- Glomerular Filtration Rate (via Exogenous Tracer Test)

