11.5 Adverse Events of Special Interest

The following events are considered adverse events of special interest based on the route of administration and toxicology profile for viltolarsen:

- Access device complication (for participants with indwelling access devices);
- Urinary protein excretion ≥ 300 mg/day based on a 24-hour urine collection;
- Serum cystatin C $\geq 1.5 \times$ baseline, or serum creatinine $\geq 2 \times$ baseline and ≥ 0.3 mg/dL, confirmed with a repeat test within 1 week of the original results (i.e., meets the cystatin C or creatinine criteria for referral to a pediatric nephrologist described in [Section 11.11.1](#));
- Any confirmed instances of hematuria or other potentially clinically significant abnormalities on urinalysis.

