12.6.1 Anthropometrics, Vital Signs, Laboratory Assessments, and ECG

Anthropometrics, vital signs, hematology, chemistry, urinalysis, and ECG results will be summarized by treatment over time using descriptive statistics for continuous outcomes. Actual values and change from Day 1 will be presented. Further, all laboratory abnormalities will be listed.

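### The proteinuria repeat is a dipstick only, so the two UPCR criteria cannot be confirmed and a boy with persistently raised UPCR can miss the mandated 24-hour collection

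*Combined protocol and SAP*

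**What the plan says.** The same rule stands in Section 9.14.1 (Sample Collection, Storage, and Shipping) and Section 11.11.1 (Monitoring of Renal Function and Urine Analyses).

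- **Trigger.** Any one of: dipstick protein ≥2+, UPCR ≥0.5 mg/mg, UPCR ≥2 × baseline, on a first morning void.
- **Repeat.** Both sections order that "a first morning void urine dipstick protein will be repeated within 1 week". UPCR is not named.
- **Gate to the 24-hour collection.** "If 1 or more of these criteria are met again on the repeat test", a 24-hour sample follows within 1 week of the results.
- **Consequence.** Section 11.11.1 refers the boy to a pediatric nephrologist if the 24-hour result is ≥300 mg/day. Section 11.5 defines the matching event of special interest as urinary protein ≥300 "mg/day based on a 24-hour urine collection".

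Table 3 lists the protein to creatinine ratio among the urinalysis analytes and, as a separate line, "Dipstick protein (to be performed by the site on the first morning void urine samples". For the scheduled voids, Section 9.14.1 adds: "An aliquot will also be sent to the central laboratory for urinalysis". That instruction is tied to the sample brought in on the day of a specified visit.

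For cystatin C and creatinine, Section 11.11.1 says instead that "the test will be repeated within 1 week of the results".

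**The concern.** The gate refers back to three criteria, but the test ordered can answer only one of them. The relative criterion shows this most clearly: a doubling from the boy's own baseline ratio cannot be read from an absolute dipstick grade.

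The rule matters because Section 2.3.2 identifies the kidney as the primary target organ in mice, rats and monkeys, and Section 11.5 bases the events of special interest partly on that toxicology. Both the proteinuria referral and the proteinuria event of special interest need a 24-hour result, so a boy who is never sent for the collection can reach neither by this route. With about 53 sites in about 19 countries, whatever is left to local judgment may be handled differently from site to site.

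This is a gap in a safety rule and not evidence of harm. Section 2.3.3 reports one Grade 2 finding of urine protein in the Phase 1/2 study and no indication of treatment-related kidney toxicity in the extension study.

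**Working it through.** The plan gives no figure to reproduce. The check is one of logic, followed by a count of how often the rule can be triggered.

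**Step 1. What each test can assess.** Let D = dipstick ≥2+, A = UPCR ≥0.5 mg/mg, R = UPCR ≥2 × baseline. The dipstick is a site test and gives D. A and R need the protein to creatinine ratio, which Table 3 lists separately under urinalysis. A dipstick-only repeat therefore assesses 1 of 3 criteria.

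**Step 2. Repeat results that should pass the gate.** Three yes/no criteria give 2³ = 8 results. Removing the one with none met leaves 7.

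| D | A | R | At least one criterion met | Recognised by dipstick alone |
|---|---|---|---|---|
| yes | no | no | yes | yes |
| yes | yes | no | yes | yes |
| yes | no | yes | yes | yes |
| yes | yes | yes | yes | yes |
| no | yes | no | yes | **no** |
| no | no | yes | yes | **no** |
| no | yes | yes | yes | **no** |

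Four are recognised and three are missed. These are counts of possible results and say nothing about how often each occurs. A boy first flagged on UPCR whose repeat dipstick is ≥2+ still goes to the 24-hour collection; the gap is confined to the last three rows.

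**Step 3. Whether UPCR is measured on the repeat by another instruction.** The central-laboratory aliquot is described for the specified-visit sample. Section 9.14.1 also says that Table 3 covers all urinalyses, but the repeat is named as a dipstick protein and not as a urinalysis. Section 11.11.1 keeps the two apart, describing the dipstick as one component of a scheduled urinalysis. Nothing in the protocol sends the repeat sample for UPCR.

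**Step 4. Comparison with the serum rule.** In the same section, a raised cystatin C or creatinine is followed by repeating the test itself, so each serum criterion can be met again. The mismatch is specific to the urine rule.

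**Step 5. Whether later visits rescue the boy.** Tables 1 and 2 schedule post-baseline first morning voids at Weeks 3, 5, 9, 13, 17, 21, 25, 29, 33, 37, 41, 45 and 49, which is 13 per boy. With 37 boys per arm, 13 × 37 = 481 scheduled samples per arm at which the rule could be triggered. The next scheduled void comes 2 weeks later (Week 3 to 5) or 4 weeks later (from Week 5 on). A raised UPCR there leads to the same dipstick-only repeat, and no void is scheduled after Week 49.

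**Step 6. Result if UPCR is added to the repeat.** All 3 criteria can be assessed and all 7 qualifying results are recognised.

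**The case against.** The strongest reply is that this is a drafting slip. The plural reference to the criteria makes sense only if UPCR is measured again, and a site could reasonably process the repeat void as a full first morning urinalysis. The laboratory manual, which is not among the documents, might already say so. The intention is plausible, but the protocol does not state it, and an unseen manual cannot be assumed to override what the protocol orders. A slip of this kind still leaves a site that follows the text exactly doing the wrong thing.

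Second, other provisions offer a safety net, some of it in mandatory wording. Section 11.11.1 requires other potentially clinically significant urinalysis abnormalities to be confirmed, and confirmed clinically significant treatment-emergent ones to be recorded as adverse events and discussed with the medical monitor. Section 11.5 includes "Any confirmed instances of hematuria or other potentially clinically significant abnormalities on urinalysis" among the events of special interest, and Section 11.7.2 brings those events to the DSMB. Section 11.11 lets the investigator repeat or add tests. Section 12.6.1 says "all laboratory abnormalities will be listed". A persistent UPCR rise can therefore become visible without a 24-hour collection. This stands, but it depends on someone judging the rise significant, and none of these provisions mandates a 24-hour collection or a nephrology referral.

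Third, the animal findings were mainly tubular, and the protocol also follows tubular urinary markers, cystatin C, creatinine and renal ultrasound, with a separate serum route to referral. This narrows what could be missed, but it does not make the proteinuria rule work.

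Fourth, the size is unknown, and one of the missed results is a doubling from a low baseline that stays below 0.5 mg/mg. A 24-hour collection in a boy aged 4 to 7 for that finding is a real burden. Both points are fair. However, the plan itself chose the doubling as a trigger; if it is thought too sensitive, the threshold should be changed openly and not filtered out by a test that cannot measure it.

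**Conclusion.** The concern holds. As written in both sections, the confirmatory step can assess one of the three criteria it is meant to confirm. A boy with persistently raised UPCR and a repeat dipstick below 2+ has no mandated 24-hour collection, and by this route reaches neither referral nor the ≥300 mg/day event of special interest.

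In logical terms, 3 of the 7 qualifying repeat results go unrecognised, and the opportunity recurs at up to 13 scheduled voids per boy. The 481 per arm is a ceiling on samples at which the rule could be triggered, not an estimate of samples in the gap. How often a raised UPCR occurs with a dipstick below 2+ is not given, so the number of boys affected cannot be computed.

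The conclusion rests on the protocol text alone and assumes that sites do what it orders and no more. A site that sent the repeat sample for UPCR on its own initiative would not have the gap. The efficacy analyses are unaffected. The correction should be made because this is a safety rule for the main toxicological target organ and the remedy is small.

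**What to change.** In Sections 9.14.1 and 11.11.1, require that both the site dipstick and the UPCR be repeated within 1 week on a first morning void, with an aliquot of that sample sent to the central laboratory. Add the matching instruction to the laboratory manual. The gate sentence then works unchanged for all three criteria, and the definition of the event of special interest in Section 11.5 needs no change.

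The cost is one phrase in each of two sections, a line in the manual, one added UPCR assay on repeat samples that are collected anyway, and possibly some additional 24-hour collections. The number of those cannot be estimated from the documents. If the burden of collections triggered only by a doubling from a low baseline is a worry, the sponsor can set a minimum absolute UPCR for that criterion, stated explicitly in the protocol.

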11.12 Monitoring and Management of Abnormal Electrocardiograms

If a clinically significant ECG abnormality occurs that was not present at baseline (screening) and the investigator determines that the abnormality is related to investigational product, the abnormality will be discussed with the medical monitor. The ECG abnormality will be monitored and evaluated with additional tests (if necessary) until the underlying cause is determined or the event is brought to an acceptable resolution. Additional clinical and laboratory information will be collected and carefully documented in order to better characterize the ECG abnormality and rule out alternative causes. ECG findings determined to be a clinically significant change from baseline should be reported as an adverse event regardless of causality. Unscheduled ECG assessments will be completed at the discretion of the investigator.

11.13 Intravenous (IV) Access Considerations

Investigational product dosing will be administered through IV infusion. Peripheral venous access (IV catheter that empties into a peripheral vein in the arms, hands, legs or feet) is the preferred route of investigational product administration for this study.

A CVA (IV catheter that empties into a large central vein) will be considered on a case-by-case basis for participants who have difficulty with peripheral venous access. A TICVAD is the preferred option of CVA, if necessary, for this study. The sponsor will decide whether or not to approve this option after discussions with the investigator and medical monitor have ensured mutual agreement that CVA will still maintain a positive benefit/risk ratio for the participant in this study. Before final decision, NS Pharma will obtain documentation from the investigator that the consulting surgeon who will place the port holds hospital privileges as a board eligible/board certified surgeon. The decision, rationale and conclusion regarding the maintained positive benefit/risk ratio will be detailed in writing and sent to the requesting site. CVA should not be implemented without sponsor approval.

An alternative method of CVA may only be considered in the case of a contraindication, in the opinion of the consulting surgeon for the placement of a TICVAD (port).

